Assessment Notes/Important Information about the family:

Elevated PHQ9 score? Yes No PHQ9 Total Score: _____

Depression resources provided Crisis Help Card provided

Referral to doctor or home visitor

Assessor/Coach Initials: _____

Risk Identification:

ATQ question #6 endorsed I don't think I can go on

PHQ9 question #9 endorsed Thoughts that I would be better off dead, or of hurting myself

Self-Harm

No plan, no intent to harm self, identifies reasons to not harm self

Lacks clear plan, states would not carry it out, identifies reasons to not harm self*

Has clear plan, means to harm self, cannot identify reasons to stop from harming self*

EMS Called* Participant called GA Crisis Line*

Contacted PI*

Child Abuse/Neglect

RPNI Completed* Safety information provided

Mandated Report Made*

Intimate Partner Violence

EMS called* Safety information provided

Referral to doctor or home visitor

Other Harm _____

Other: _____ **None**

**Must record in AE/SAE Log (on Google docs)*

Consult Needed: Yes No Date/time supervisor was consulted: _____
if you identified any risk above, a consult is needed

Is this a possible AE or SAE? Yes No AE/SAE #: _____

Report of clinical issue being addressed (List each issue one at a time and how it was addressed):

Report of consultation (what information was given to supervisor, what action needs to be taken, how did participant respond, what intervention was implemented, etc.):

Supervisor Comments (follow up steps needed, additional information, etc.):

Assessor/Coach Signature

Date

Supervisor Signature

Date

When complete, scan and email to [name] for filing and circulation to project team

Assessment Data Checklist

ID#: _____

PRE

POST

Date: _____

Before you leave the home:

Sprint signal: Successful Unsuccessful/Ineligible N/A

Questionnaire: Part 1 Part 2 Checked for missing data

Observation data

ASRI: Followed up for any endorsed safety questions

Safety Monitoring Forms (only used for participants with potential safety concerns)

iPhone Customization Questionnaire

Changes in Contact Information _____

Best times for calling to schedule/confirm training visit _____

Initial and date when items are complete: Initials: _____ Date: _____

At the office:

Enter Assessment Information into Access Database (S: drive)

Update Matriculation Table (Google docs)

Assessment Summary & Risk Identification completed and signed

- Email to supervisor if there is a safety concern

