If there is a **clear plan and no protections** (E above), proceed to **Box #1**.

If there is a **plan but person identifies protections from acting** (E above), proceed to **Box #2**.

If the person **has no plan, says they would not act** on the plan, and can **tell you why** they wouldn't act on the plan (e.g., I would never do that to my baby. I couldn't stand the thought of her not having a mom), let mom know "**I am glad to hear that!**" then proceed to **Box #3**.

1. Highest Risk:

Person states that:

- They are thinking about suicide
- They have a clear plan (how, when, where)
- Means are available (guns, pills, nobody home, etc.)
- They cannot identify things stopping them from carrying out their plan

2. Medium Risk:

Person acknowledges thoughts about suicide but

- Lacks a CLEAR plan
- States that they would not carry it out and identifies reasons why they wouldn't

3. Lowest Risk:

Person is showing signs of depression but denies any thoughts about self-harm/suicide OR

- Has had thoughts but **NO plan** and says they would **not do it** and identifies reasons why they wouldn't

- Do Not leave person alone unless your safety is threatened
--Text and Call your supervisor until you make contact (wait at least 30 minutes before intervening)

- If your safety is threatened, go to nearest safe place, call 911 & state exact concern
--Text and Call your supervisor for immediate support
--Do not leave until told by EMS that they do not need to speak to you at the scene.

3. If you cannot reach a supervisor and must intervene, do the following:

- Stay calm, be empathetic, and state your concern ("I'm concerned about your safety")
- State that the person needs to "see a doctor right away" /can share "Postpartum Depression Facts & Stories" and "Crisis Help Card"
- Give 3 choices and follow through
 - They can call 911 and ask for a ride to nearest hospital for emergency behavioral health services to find a way to feel better/not hurt self
 - You can place the call to 911
 - They can have another adult join the 2 of you and the other party can sign notification form to get help.
 - They can call the Georgia Crisis & Access Line [name]

- Use gentle, reflective & empathetic statements. Be clear that you are "not a therapist, but there are people out there who can help." Share "Postpartum Depression Facts & Stories" and encourage the person to share booklet with and talk to doctor.

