- Share "Crisis Help Card" and offer to sit with mom while she contacts the Georgia Crisis & Access Line [name]

- Document on the **Assessment Summary and Risk Identification** exactly what the concerns were, what you did, and the mom's responses. Do not include identifiers. Email to Clinical Supervisor and **notify by text that you have done so.**

- "From the results of our assessment it looks like you might be experiencing Depression. I am not a therapist and I can't diagnose but there are people out there who can help. I wonder if anyone has ever talked with you about Depression." [Pause and give mom a chance to comment if she wishes] Share "Postpartum Depression Facts & Stories" and encourage the person to share booklet with and talk to their doctor or their baby's doctor at the next well child visit.
- Document on the **Assessment Summary and Risk Identification** exactly what the concerns were, what you did, and the mom's responses. Do not include identifiers. Email Supervisor. If you don't receive a signature reply within 24 hours, text and call. File signed copy + all other documentation in mom's folder within 72 hrs.

V. Adverse Event Guidelines

MOM & BABY NET GUIDELINES FOR ADVERSE EVENTS AND SERIOUS ADVERSE EVENTS:

General Notes:

AEs and SAEs are events that occur during the course of the participant's involvement in the project; that is, between signing the consent form and before completion of the final assessment.

Each AE and SAE will be recorded in the Adverse Events log, which will be reviewed weekly during supervision. The log must be updated on a regular basis to ensure accurate recording of events. Coaches and Assessors will fill out a clinical case note form and have them signed off by a supervisor within 48 hours (in some cases, additional forms will be required). The information contained in the Clinical Case Note Form will be entered into the AE log.

A unique tracking number will be assigned to each AE and SAE for reporting purposes. The tracking system will identify if the incident is an AE or an SAE and the next chronologically assigned number. For example, when the first AE is reported, it will be identified by "AE-01." If the next incident reported is an SAE, it will be identified by "SAE-01." The next AE would be identified by "AE-02" and so on.

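### The self-harm decision tree and the risk form are contradictory or silent for at least 3 of 6 combinations of plan and reasons not to act

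*Protocol*

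**What the plan says.** The tree (Protocol, IV. Safety Monitoring Documents, Risk of Self Harm – Decision Tree) applies when a mother endorses a self-harm item or raises the subject herself. Staff ask about method, access, place and what keeps her from acting. Three printed texts then classify her.

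- **Routing sentences.** A clear plan with no protections goes to Box 1. A "plan but person identifies protections from acting" goes to Box 2. A mother who "has no plan, says they would not act" and can give the reason goes to Box 3.
- **Box descriptions.** Box 1 (highest) needs suicidal thoughts, a clear plan, available means, and "They cannot identify things stopping them from carrying out their plan". Box 2 (medium) needs thoughts in a mother who "Lacks a CLEAR plan", would not act and gives reasons. Box 3 (lowest) covers a mother who denies thoughts, or who has thoughts, no plan, no intention to act and reasons.
- **ASRI self-harm rows** (II. Consent & Assessment Manual, Assessment Summary & Risk Identification). Row 1 reads "No plan, no intent to harm self, identifies reasons to not harm self". Row 2 is no clear plan, would not act, has reasons. Row 3 is a clear plan, means, and no reasons.

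The action blocks are printed after all three boxes. In print order, the first says "Do Not leave person alone unless your safety is threatened". The second has staff "offer to sit with mom while she contacts the Georgia Crisis & Access Line". The third has staff share a booklet, document the concern and email the supervisor, with a follow-up if they do not "receive a signature reply within 24 hours, text and call".

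Separately, the ASRI instructions call for immediate contact when a risk is identified at any time in the study, and the form requires a consult for any risk ticked.

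**The concern.** A triage rule should give each foreseeable set of answers exactly one level, because the level selects what staff do next. Staff here must tell the mother that they are not therapists, and the tree itself provides for the case where no supervisor can be reached. The rule then has to work unaided.

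The cells in question are foreseeable. Mothers enter the trial on a positive depression screen. Any PHQ-9 item 9 response of several days or more starts the follow-up, at home or on a remote call. The question about what holds her back is scripted, so an answer of nothing must be expected. The tree provides for that answer only when the plan is clear.

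If the action blocks belong to the boxes in print order, the choice runs from staying with the mother to a booklet and an email. A mother with a clear plan who names a reason is sent to a box whose description excludes her. A mother with thoughts, no clear plan and nothing to stop her is sent to no box.

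**Working it through.** The documents state no figure on this point, so the check is an enumeration.

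**Inputs.** The three routing sentences and three box descriptions come from the Decision Tree, and the three self-harm rows from the ASRI. Plan has three states, following the documents' own distinction between a clear plan, no clear plan and no plan. Reasons not to act are named or not named. That gives 3 x 2 = 6 cells.

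**Assumptions.** Thoughts are acknowledged, naming reasons goes with saying she would not act, and means are available (varied below). A plan in the second routing sentence may be clear or unclear.

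| Plan | Reasons | Routing | Box text | ASRI row | Result |
|---|---|---|---|---|---|
| Clear | Not named | Box 1 | Box 1 | Row 3 | Consistent |
| Clear | Named | Box 2 | None | None | Contradiction |
| Unclear | Named | Box 2 | Box 2 | Row 2 | Consistent |
| Unclear | Not named | None | None | None | Gap |
| None | Named | Box 3 | Box 3 (also Box 2 if read literally) | Row 1 (also row 2 if read literally) | Depends on reading |
| None | Not named | None | None | None | Gap |

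**Why the three cells fail.**

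- *Clear plan, reasons named.* Box 1 and row 3 require that she has no reasons. Box 2 and row 2 require that the plan is not clear. Box 3 and row 1 require no plan. Only the routing sentence places her.
- *Unclear plan, no reasons, and no plan, no reasons.* Routing to Boxes 2 and 3, the Box 2 and 3 descriptions (apart from denial of thoughts) and rows 1 and 2 all require reasons. Routing to Box 1, the Box 1 description and row 3 all require a clear plan.

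**Counts, means available.** Failing under either reading: 1 contradiction + 2 gaps = 3 of 6.

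- If no plan with reasons is taken as Box 3, where routing, Box 3 and row 1 agree: 6 − 3 = 3 of 6 consistent.
- If lacking a clear plan is read to include having none, that cell also fits Box 2 and row 2: 6 − 4 = 2 of 6 consistent.

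**Means not available.** Routing still sends a clear plan without reasons to Box 1, but Box 1 and row 3 both require means. That cell then fails too, which leaves 3 − 1 = 2 of 6 or 2 − 1 = 1 of 6 consistent.

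**Narrower routing.** If the second routing sentence meant only an unclear plan, a clear plan with reasons would have no level in any text. The contradiction would become a third gap, and the count of 3 would stand.

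**The case against.** **Supervisor contact is mandatory.** The ASRI requires immediate contact and a consult for any identified risk, and the assessment procedures tell staff to call the supervisor and stay if there is immediate crisis. A reader might infer that a mother in a gap cell has no assigned action. The documents do not support that. What remains is that none of these duties gives a level or says which action block to follow meanwhile. The remote step lists (VI. COVID Remote Procedures, Immediately After Pre-Assessment Call(s) and the post-assessment equivalent) ask only that the ASRI be emailed when self-harm is endorsed, although the ASRI's own instruction on immediate contact still applies.

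**Clear plan with reasons does have a level.** Routing gives Box 2. That is right on the wider reading of the sentence, but staff who follow it arrive at a description that contradicts what they have just heard, and the form has no row for it. The form's free-text fields can record her answers, but they do not settle the level.

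**Only 2 of 6 work.** A reader might prefer this harsher count. It needs a literal reading of Box 2 that the page's contrast between an unclear plan and no plan does not favour.

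**Adverse event logging.** A reader might infer that the same answers lead to different logging, because row 2 carries a must-log mark and row 1 does not. That depends on the same literal reading. In any case, the ASRI asks whether the event is a possible adverse event, the After Home Visit steps send possible events to the log, and the Adverse Event Guidelines require every one to be recorded.

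**Layout.** The page may have been a flowchart, and the pairing of action blocks with boxes is inferred from print order. The six-cell comparison does not use that pairing.

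**Conclusion.** The point holds in this form: at least 3 of 6 combinations are contradictory (1) or uncovered (2) under every reading tested. One consistent level is given for 3 of 6 on the ordinary reading and 2 of 6 on the literal one, both with means available. The result rests on printed sentences. The three plan states are an analytic construction, but they follow the documents' wording.

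The consequence is a missing or conflicting level and the missing on-the-spot instructions that go with it, softened by the required supervisor contact. The documents give no rate of suicidal thoughts, so no number of affected mothers can be stated, and no effect on any trial estimate is claimed.

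**What to change.** Replace the routing sentences and box descriptions with one grid:

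| Plan | Names reasons | Names no reasons |
|---|---|---|
| Clear | At least medium, with live supervisor contact | Highest, whether or not means are available |
| Unclear | Medium | At least medium, with live supervisor contact |
| None | Lowest | At least medium, with live supervisor contact |

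Live contact means reaching the supervisor before staff leave the home or end the call, so the rule also covers remote assessments. Mothers who deny any thoughts stay at the lowest level, as now. Print the action block for each level beside it, and print the same levels on the ASRI. No change to adverse event logging is needed.

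The cost is one redrawn page and one form edit, with no new data. The design statement describes randomization in the past tense. If contact with participants has ended, the change serves only later use of the manual.

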- c. *We will begin the questionnaire going through questions together.* Start the questions together. Read each question for mom and allow her to choose an answer. Pay attention to how mom is doing comprehending questions and answers.
 - i. If she seems to be comprehending well, find a good point to ask if she would like to continue on her own or continue going through together. If she wants to continue on her own, remind her to stop at the pictures so you can review instructions.
 - ii. If she seems to be comfortable going through questions together, continue that way.
6. When mom reaches STOP sign she will hand iPad back to assessor. Click submit to check for safety concerns and skipped questions.

CHECK QUALTRICS FOR POTENTIAL SAFETY CONCERNS & SKIPPED QUESTIONS

1. When mom hands back the iPad, click 'Next' to see flagged questions related to self-harm.
 - a. If self-harm question(s) are endorsed, use Decision Tree to follow up.
 - i. ATQ #6 – I don't think I can go on
 - responses of moderately often, often, or all the time
 - ii. PHQ9 #9 – Thoughts that you would be better off dead, or of hurting yourself
 - responses of several days, more than half of the days, or nearly every day
 - b. NOTE: If someone is in immediate crisis, call your supervisor. Do not leave the home.
2. Check Qualtrics report for missing or skipped items. Tell mom you want to double check any missing responses and make sure nothing was skipped by mistake.
 - a. If questions were skipped on purpose, leave blank.
 - b. If questions were skipped my mistake, add the mom's new responses (edit survey option).

PREPARE FOR VIDEO RECORDING

1. *Now we are going to make a video of you and your baby as you interact together. There will be two parts to the video. We'll start with whatever you and your baby want to do together, then I'll share some books that you and your baby can look at together.*
2. Setting up for the interactions:
 - o **Setting the Stage:**
 - i. **Let mom know that we need a relatively quiet place with plenty of light.**
 - o The space should be **away from others** so that the interactions will not be interrupted by other people in the home
 - o If possible, pick a room **away from sources of noises** that could be picked up on the camera's microphone (**like a noisy kitchen, television, or street**)

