 - c. 2 video recordings
 - d. Confirm Family information and alternative contacts
3. Share materials with mom if necessary per safety decision tree
 - a. Referral to talk with doctor and/or home visitor (if PHQ9 score is 10+)
 - b. Postpartum Depression Facts
 - c. Crisis Help Card (if flagged item(s) on questionnaire were endorsed)
4. Schedule training visit to bring her iPhone to get her started in the program. NOTE: allow more time if she is in crisis or other anomalies arise that may require more time to sort out. She should plan for 1.5 hour for training – preferably when baby is asleep or another adult is at home to help with other children.
 - a. Open Google Calendar on iPad
 - b. Ask mom for best times for future calls or visits. Schedule day and time if possible and add to Google calendar using ID number ('Training Visit ID ####')

c. Confirm with mom the best numbers to call with a visit reminder or to schedule training visit (if unable to schedule now)

AFTER HOME VISIT

1. Update Access Database:

a. If applicable, update “Best times to call” under Notes in the “Tracking Information Form”

If this is a new Mom, you can click in the Date Received box and start entering data.
If this is an existing Mom, use the drop down box to the right to look up Mom's

Mom ID	(New)	Date Received	Referral Source
Study Status		Attrition Reason	Please specify other:
Mom First Name		Mom Last Name	Marital Status
Street Address		Other Address	Cell Phone
City		State	Home Phone
Mom Birthdate		Postal Code	Primary Language
Baby's Name		Baby's Birthdate	Work Phone
Email			
Notes			
Mom Baby Net App Tracking Information			
UserName:  Password: 			

b. Update Scheduled Appointments: Change “Status” from “SCHEDULED” to “COMPLETE.” Check the boxes “Q1” and “Interactions” accordingly.

Scheduled Appointments

Mom ID	Type	Date	Appointment Details	Assessor	Status	Check the Completed Assessments	Notes
101	Pre	4/8/2015	9:00 AM	[name]	Scheduled	   	
*					Completed	   	
*					Cancelled	   	
*					Rescheduled	   	

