- 4 Get treatment for your depression. You can feel better.

Crisis Help Card

What's Going On?	What Should I Do?

It's a life-threatening emergency:
 
• Someone needs medical attention• You have hurt yourself• You are in danger of hurting yourself	
CALL 911

It could become an emergency day or night:
 
• You are having thoughts about hurting yourself but will not act on them• You are safe right now but afraid that you might hurt yourself in the future	
Contact the National Suicide Prevention Line suicidepreventionlifeline.org or [name]
 
Or the Georgia Crisis and Access Line mygcal.org or [name]
 
These are 24-hour, toll-free, suicide-prevention services available to anyone in suicidal crisis
 

You need help; it's not an emergency
 
• You feel sad, frustrated, or discouraged	
Talk to your coach on your next call
 
Message your coach to let her know you want to talk with her about this on your next call

III. Coach Manual

Mom & Baby Net Training Visit Procedures

- **BEFORE HOME VISIT**
- **RESCHEDULING**
- **DAY OF HOME VISIT**
 - **BEFORE ARRIVING**
 - **ARRIVE AT HOME**
 - **CONDUCT TRAINING**
 - **BEFORE LEAVING THE HOME**
- **AFTER HOME VISIT**

BEFORE HOME VISIT

1. Check Outlook calendar to confirm participant ID#, date, and time of assessment.
2. Look up participant in Access database to confirm names, address, field partner, and check for any notes specific to the assessment.
3. Contact the participant
 - a. Confirm the time and place; see RESCHEDULING below if needed.
 - b. Prepare mom for what to expect during the visit
 - 1-1.5 hour visit duration
 - Prepare mom for session. She will receive the iPhone and we will get familiar with the iPhone, program app, and begin the first session together.
 - Visit will go most quickly and smoothly if there is someone in the home who can care for baby and other children; we understand that this is not always possible and we will work with you if this can't happen, but it does make the process go faster during the visit
 - c. Ask if there are any questions
 - d. Let her know we are looking forward to meeting her and her baby
4. Print out map-quest map/directions or use navigator.
5. If applicable, contact field partner and confirm where/when you will be meeting for the assessment
6. Prepare for visit:

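### The self-harm decision tree sets a 30-minute minimum before staff act, apparently for the highest-risk mother, when no supervisor answers, and writes no exception for imminent danger to her

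*Protocol*

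**What the plan says.** Protocol Section IV (Risk of Self Harm – Decision Tree) sorts a mother who reports thoughts of death or suicide into three boxes. The first group of actions after the boxes has staff stay with her unless they are themselves threatened, and adds: "Text and Call your supervisor until you make contact (wait at least 30 minutes before intervening". Two further instructions follow in that group:

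- For staff under threat: "If your safety is threatened, go to nearest safe place, call 911 & state exact concern".
- For the mother: "If you cannot reach a supervisor and must intervene, do the following". Under this step staff are to "Give 3 choices and follow through"; a 911 call placed by staff is one of the options listed.

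Four other places bear on the point:

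- Section II, in the check of Qualtrics for safety concerns: "NOTE: If someone is in immediate crisis, call your supervisor. Do not leave the home".
- Section II, Before Leaving the Home, lists among materials to share: "Crisis Help Card (if flagged item(s) on questionnaire were endorsed". The card classes "You are in danger of hurting yourself" as a life-threatening emergency and tells the mother to call 911.
- The Assessment Summary & Risk Identification form tells staff to contact the named lead at once when a risk is found. Under self-harm it has boxes for EMS having been called, the mother having phoned the Georgia crisis line, and the PI having been contacted.
- Section VI (COVID Remote Procedures) sends the coach to the same tree after each self-harm item, at pre- and post-assessment.

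**The concern.** The trial enrols mothers because they screen positive for depression, and it asks about self-harm before and after the programme. Positive answers are therefore foreseeable, and the tree is what a non-clinician staff member will follow when one occurs. If a mother has a plan, the means and no reason to hold back, and nobody answers the supervisor's phone, the written instruction is a minimum delay. Nothing beside it says that the delay lapses when she is about to act. The possible consequence is a death. No quantity in the SAP depends on this; it is a matter of participant safety.

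**Working it through.** No formula applies beyond a count, so the check sets the texts side by side.

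**1. Which mother does the wait concern?** Three risk boxes are followed by three groups of actions of falling intensity:

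- staying with her, 911 and EMS;
- empathetic statements, the help card and an instruction to "offer to sit with mom while she contacts the Georgia Crisis & Access Line";
- telling her she may be depressed and giving her the booklet.

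If the first group did not belong to Box #1, the highest-risk box would have no matching actions. The link is strong, but it is inferred.

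**2. When does the wait bind?** Only until a supervisor is reached, since a supervisor who answers can direct help immediately.

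- Supervisor answers at once: hold = 0 minutes.
- No supervisor answers: hold = at least 30 minutes.

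**3. Is there a written exception for imminent danger to the mother?**

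| Place | What it provides | Waives the wait for her danger? |
|---|---|---|
| Tree, line on threat to staff | Outright order to call 911 | No; trigger is danger to staff |
| Tree, intervention step | Staff 911 call as one option | No; requires that the supervisor cannot be reached, and gives no test for when staff must act |
| Section II immediate-crisis note | Call the supervisor and stay | No; names only the supervisor |
| Risk identification form | Immediate contact with the lead; boxes for EMS and PI | No; it foresees EMS but does not address the wait |
| Crisis Help Card | Call 911 | No; addressed to the mother, not staff |
| Section VI, remote checks | Refer to the tree | No |

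Written exceptions found: 0. For the same danger, the card sends the mother straight to 911 while the tree gives staff a minimum delay.

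**4. Remote checks.** 2 items (PHQ9 #9 and ATQ #6) × 2 assessments (pre and post) = 4 checks. All 4 use the tree unchanged. None asks the coach to confirm where the mother is when an item is endorsed.

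**The case against.** The strongest reply is that the intervention step is itself the override: staff who judge that they must act may do so, and a 911 call is among their options. That may well be the intent. But the step's written condition still includes failure to reach the supervisor, it gives no criterion, and it does not cancel the 30 minutes. Staff who are told to say that they are not therapists need clearer wording.

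Second, the chart was flattened, so the match to Box #1 is not shown on the page. The contents list also names a decision tree under Section V, and none appears in that section's text; it may be this one misplaced, or a figure lost in extraction. Both points stand as limits on certainty.

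Third, EMS is clearly foreseen on the risk form, and staff are not idle: they stay with the mother and keep calling. This stands, and it rules out any claim that emergency help for her was overlooked.

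Fourth, the remote gap is smaller than it looks. Staying with her translates to staying on the line, and the offer to sit with her is in what appears to be the medium-risk group. Addresses are confirmed before the remote assessment, and crisis numbers are loaded on the project phone. A reader might grade the four checks by whether they share a call with the reminder about the filming spot. The documents do not support that: the reminder concerns privacy, noise and light, and confirms no address on any call. The remote point is therefore a secondary suggestion.

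**Conclusion.** The point holds in a limited form. When no supervisor can be reached, the tree as written holds staff back for at least 30 minutes with what is very probably the highest-risk mother, and no text provides for imminent danger to her. This should be changed.

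A reader might infer that every highest-risk mother waits half an hour, or that staff may not call 911 for her. Neither follows. The hold ends when a supervisor answers, and a staff call is an available option once the intervention step applies.

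The conclusion rests on three assumptions: the first group of actions belongs to Box #1, the parenthesis is meant as a minimum, and no exception was lost with the chart's layout. Supervisor response times and the number of mothers meeting Box #1 are not in the documents, so the number affected cannot be estimated.

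**What to change.** In the Section IV tree, delete the 30-minute minimum for highest risk. State instead: for a mother who meets the Box #1 criteria, if no supervisor answers at once, or if she is about to act, staff call 911/EMS or connect her to the crisis line immediately, and go on contacting the supervisor or PI in parallel. Tying the rule to the Box #1 criteria avoids a new undefined term. Keep supervisor-first for the other two boxes, and make the Section II immediate-crisis note match.

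As a secondary change, add one remote line and cite it at the four checks in Section VI: stay on the call; when an item is endorsed, confirm the mother's current address and a callback number; have staff place any 911 call to that address. Do not bring in her alternate contacts unless she agrees. Those names were collected to trace her, and a call could disclose suicidality to someone unsafe; partner violence is itself a listed risk on the study's form.

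The cost is at most about a page of text and a short staff briefing, plus some emergency calls that a supervisor would have judged unnecessary.
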